2. OBJECTIVES AND ENDPOINTS

2.1. Primary Safety Objective

To determine the safety and tolerability of orally administered ENT-01 for approximately 14 weeks in subjects with Parkinson's disease-related constipation.

Safety endpoints will include adverse events as evaluated with subject self-reporting, vital signs, clinical chemistry and hematology blood analyses, urinalysis, and electrocardiogram (EKG).

During the dosing period, it is anticipated that no more than 2 subjects out of 50 (4.0%) will have an adverse event of grade 4 or 5 that is at least possibly related to ENT-01. Should there be more than 2 subjects with an adverse event grade 4 or 5 that is at least possibly related to ENT-01 in the cohort of subjects, the study will be put on an immediate clinical hold. Safety Monitoring processes are identified in [Section 10.14](#).

In addition, individual safety stopping rules will include:

- Reaching dose-limiting tolerability (DLT) before a prokinetic effect
- Having a non-DLT gastrointestinal adverse event > grade 3 within 24 hours of taking study medication that is at least possibly attributable to ENT-01

Tolerability

Tolerability endpoints are referred to as the DLT and will include:

- Recurrent vomiting defined as 3-5 episodes of vomiting within 24 hours of taking study medication (i.e., a Grade 2 or higher AE, see [Table 2](#)).
- Recurrent diarrhea defined as 7 episodes of diarrhea within 24 hours of taking study medication on 2 consecutive days (i.e., a Grade 3 or higher AE, see [Table 2](#)).
- Dizziness defined as lightheadedness or fainting on rising from lying to sitting or standing that requires non-urgent medical intervention within 24 hours of taking study medication. (i.e., a Grade 2 or higher AE see [Table 2](#)).

It is anticipated that all subjects will exhibit a prokinetic effect at a dose lower than DLT and less than or equal to 250mg. Subjects reaching DLT before a prokinetic effect will be treated at the highest dose at which they did not experience a DLT.

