Study Product, Dose, Route, Regimen	ENT-01 will be administered in tablet form, once daily, on an empty stomach, first thing in the morning, with 8 oz of water. No food intake will be allowed for 60 minutes after taking medication. The tablets will be 25mg each. Subjects will begin dosing at the same dose level they were stratified to in the ENT-01-030 randomized study (i.e. , starting at either 3 tablets or 6 tablets,) and escalate up to a pro-kinetic dose or a maximum dose of 250mg.
Study Endpoints	
Safety Endpoints: Adverse events as evaluated with subject report, vital signs, chemical chemistry and electrocardiograms (EKG).
 
Tolerability Endpoints:
 
 • Recurrent vomiting defined as 3-5 episodes of vomiting within 24 hours. • Recurrent diarrhea defined as 7 episodes of diarrhea within 24 hours for 2 consecutive days. • Dizziness defined as lightheadedness or fainting on rising from lying to sitting or standing and severe enough to require non-urgent medical intervention within 24 hours. 
Primary Efficacy Endpoint:
 
 • Change from baseline in weekly CSBM rate during the 12 weeks of treatment over baseline. 
Secondary Efficacy Endpoints:
 
 • Change from baseline in the MDS-UPDRS score at the end of the 12-week fixed dose period. • Change from baseline in cognition as assessed by the MMSE at the 12-week fixed dose period.

	
 Change from baseline in psychosis as assessed by the SAPS-PD score at the 12-week fixed dose period.

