A Phase 2a study involving 50 patients with Parkinson's disease and constipation was recently conducted (RASMET; IND 130770, NCT03047629). The purpose of the study was to assess the safety, tolerability, pharmacokinetics, and pharmacodynamics of orally administered medication to relieve symptoms of constipation associated with Parkinson's disease. The study consisted of an 8 to 12-week Stage 1 period, and an 8 to 10-week Stage 2 period. All subjects received the study drug during one of the observational periods of the study. The study evaluated the safety of ENT-01, and its effect on bowel function and neurologic symptoms.

In Stage 1, 10 patients received escalating single doses from 25 to 200 mg/day or maximum tolerated dose (MTD). The goal was to determine safety and tolerability. In Stage 2, 34 patients received daily doses escalating from 75 to a maximum of 250mg/day, a dose that induced change in bowel function or MTD, followed by a "fixed" dose for 7 days, and a 2-week washout. Primary efficacy endpoint was defined as increase of 1 complete spontaneous bowel movement (CSBM)/week, or 3 CSBM/week over 14-day baseline period. Safety was also assessed.

In Stage 2, 82.4% patients achieved the primary efficacy endpoint. Mean CSBM/week increased from 1.2 at baseline to 3.6 during fixed dose ($p=1.2\times10^{-7}$) (Hauser et al., 2019). Common adverse events included nausea in 21/44 (47%) and diarrhea in 18/44 (40%) patients. No study-drug related serious adverse events were reported. The only SAE was a GI bleed after medication was discontinued in one patient. This patient was on aspirin, Plavix, and Motrin, and the SAE was considered unrelated to study medication. There were no deaths. The only other noteworthy AE was dizziness 8/44 (18%). Dizziness was graded as moderate in one patient who was receiving an alpha-adrenergic blocking agent (Terazosin). This patient was withdrawn from the study and recovered spontaneously. All other AEs resolved spontaneously without discontinuation of ENT-01. The details of the RASMET study AEs are in the study report contained in IND 130770.

Significant and lasting improvements were observed in total MDS-UPDRS scores ($p=0.0008$), the MDS-UPDRS-Part III scores (motor component) ($p=0.0006$), cognition (MMSE) ($p=0.0004$), hallucinations, sleep, and circadian rhythm ($p=0.016$). Hallucinations improved in 5/6 patients. Systemic absorption was $< 0.3\%$.

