The dose will be taken upon awakening on an empty stomach along with 8 oz. of water. Subjects prescribed levodopa should wait at least 30 minutes between taking levodopa and study medication. The subject will be instructed to not eat for at least 60 minutes after study drug administration. Tea, coffee with/without milk/sugar and orange juice (without pulp) are permitted. Plain yoghurt can be added if the patient experiences repeated nausea. Dosing will be increased every 2-3 days until a pro-kinetic dose or the maximum dose is reached. If the subject has not

produced a CSBM within 24 hours on at least 4 of 5 consecutive days, then they will increase their daily dose by 1 tablet (by 25 mg). This incremental dosing will continue until the subject:

- reaches the prokinetic dose (the dose producing a CSBM within 24 hours on at least 4 of 5 consecutive days). The subject then remains on that dose until Visit 4;
- reaches the maximum dose of 10 tablets (250mg for active treatment); or,
- reaches the dose limiting tolerability (DLT).

If the subject has 7 or more discrete episodes of diarrhea separated by 30 minutes or more within 24 hours at any dose on 2 consecutive days, the dose will be reduced by 25mg and fixed at that dose (assuming the diarrhea abates at the lower dose).

Should a prokinetic response not occur at the maximum allowed number of tablets (10 tablets or 250mg), subjects will continue to take 10 tablets throughout the Fixed Dose period.

Site staff will review subject diary entries daily and contact subjects as needed to ensure subject safety, compliance with study and dosing instructions, and to determine the subject's individual fixed dose level. The day that a subject "fixes" their dose for the first time (as determined by site staff) is considered Day 1 for the purposes of scheduling subsequent study visits.

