10.15. Stopping Rules

It is anticipated that no more than 2 subjects out of 50 (4.0 %) will have an AE of Grade 4 or Grade 5 that is at least possibly related to ENT-01 in this Study. Should there be more than 2 subjects with an AE grade 4 or 5 that is at least possibly related to ENT-01 in the cohort of subjects, the study will be put on an immediate clinical hold. Safety Monitoring processes are identified in [Section 10.14](#).

In addition, individual safety stopping criteria will include:

- Reaching DLT before a prokinetic effect
- Serious Adverse Event at least possibly attributable to ENT-01.
- Having a non-DLT gastrointestinal adverse event > grade 3 within 24 hours of taking ENT-01 that is at least possibly attributable to ENT-01
- A fall in systolic blood pressure to < 80 mm Hg upon rising from lying to sitting or standing
- A fall in diastolic blood pressure to < 40 mm Hg upon rising from lying to sitting or standing

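### A DLT before a prokinetic effect is both a stopping rule and a reason to continue at a lower dose, and the diarrhea DLT that is tabulated differs from the one defined and used for dosing

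*Combined protocol and SAP*

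**What the plan says.** **Action after a DLT.** The individual safety stopping rules in Section 2.1 include "Reaching dose-limiting tolerability (DLT) before a prokinetic effect". Section 10.15 repeats the item as "Reaching DLT before a prokinetic effect". The next item in that list is "Serious Adverse Event at least possibly attributable to ENT-01", and the list ends with two blood-pressure limits on rising. Section 2.1 closes with a different instruction for the same subjects: "Subjects reaching DLT before a prokinetic effect will be treated at the highest dose at which they did not experience a DLT".

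Section 3.2 gives three ends to dose escalation: the prokinetic dose, the 250 mg maximum, or that the subject "reaches the dose limiting tolerability (DLT". For diarrhea it adds an action: "the dose will be reduced by 25mg and fixed at that dose (assuming the diarrhea abates at the lower dose".

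**Diarrhea threshold.**
- Synopsis: "Recurrent diarrhea defined as 7 episodes of diarrhea within 24 hours for 2 consecutive days". Section 2.1 uses the same count and duration, timed from intake of study drug.
- Section 3.2, dose-reduction trigger: 7 or more discrete episodes in 24 hours, two days running. A separate sentence takes off one tablet for repeated diarrhea and gives no count.
- Section 10.4: more than 7 episodes within 24 hours, with no second day required. Section 11.4 takes its tolerability endpoints from 10.4.

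**Blood pressure.** Section 10.4 includes systolic below 80 or diastolic below 40 mm Hg in the dizziness DLT. Section 10.15 lists a fall to the same values on rising as a separate stopping criterion.

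**The concern.** Two instructions cover one safety event and lead to opposite actions. A site that follows the stopping lists takes the subject off study drug. A site that follows the closing sentence of 2.1, or 3.2, keeps the subject on drug at a lower dose through the Fixed Dose Period. Up to 20 sites may have to choose. Section 13.9 requires exact adherence and allows no waivers, so obeying one sentence can look like a deviation from the other.

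The diarrhea mismatch raises a reporting problem. Tolerability is part of the primary safety objective, and the Background names local GI toxicity as the main safety focus. If the tolerability table uses a different threshold from the one that changes doses, it can count events that did not meet the dosing rule and miss events that did.

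**Working it through.** **1. The plan's own figure.** The only sample-size figure is a 92% chance of seeing at least one AE with a true rate of 5% among 50 patients (Section 11.7). Check: 1 − 0.95^50 = 0.923. It reproduces, and nothing below depends on it.

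**2. One subject with a DLT before a prokinetic effect, under each text.**

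| Text | Consequence |
|---|---|
| 2.1, stopping list | Stop; what is stopped is not stated |
| 10.15, stopping list | Stop; listed beside related SAEs and blood-pressure limits |
| 2.1, closing sentence | Continue at the highest DLT-free dose |
| 3.2, ends of escalation | Escalation ends; no discontinuation stated |
| 3.2, diarrhea rule | Reduce by 25 mg and fix, if the diarrhea abates |
| Section 6, discontinuation | DLT not mentioned |

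No row says which text prevails, and none says that stopping refers to escalation only. Only diarrhea has an explicit 25 mg step-down; vomiting and dizziness do not. A DLT at the 75 mg starting dose has no lower dose in Table 1, so the closing sentence of 2.1 cannot cover every case.

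**3. Size per affected subject.** Stop reading: 0 further days. Continue reading: up to 12 weeks × 7 = 84 days at a lower dose.

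**4. Diarrhea definitions compared.** Let a and b be the episode counts on two consecutive days.
- Two-day dosing rule (3.2): a ≥ 7 and b ≥ 7. The synopsis and 2.1 give the count simply as 7; read as at least 7, they agree with 3.2.
- Tabulated DLT (10.4, used by 11.4): a > 7 or b > 7.

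| Counts (a, b) | Two-day dosing rule met | DLT in the table |
|---|---|---|
| 7, 7 | yes | no |
| 8, 0 | no | yes |
| 8, 6 | no | yes |
| 7, 8 | yes | yes |
| 8, 8 | yes | yes |
| 7, 0 | no | no |
| 6, 6 | no | no |

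Neither definition contains the other. They differ in count (7 or more versus more than 7) and in duration (two days versus one).

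**5. Blood pressure.** A reading below the limit on rising is a DLT under 10.4. If it comes before a prokinetic effect, the closing sentence of 2.1 points to step-down, while 10.15 lists the fall as a stop in its own right.

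**The case against.** The best reply is that stopping means stopping escalation. Section 2.1 states the action for exactly these subjects, in the same section as the rule. Section 3.2, the operative dosing text, puts a DLT beside the prokinetic and maximum doses as an end of escalation. The qualifier about a prokinetic effect also fits an escalation rule; as a withdrawal rule it would oddly spare a DLT that came later. Section 6 does not name DLT, although it names no specific events at all. This stands as evidence of intent: step-down and fix is probably what was meant. It does not settle the text. Section 10.15 lists the item among events for which stopping the drug is the natural reading, and no sentence narrows it.

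Second, the 3.2 diarrhea paragraph is a dose-reduction trigger and does not call itself a DLT definition. That is correct, and it is treated as a trigger here. The uncounted rule in 3.2 could also lead a site to reduce the dose after 8 episodes on one day. So the 8-then-0 case shows only that the two-day rule is not met, not that the dose stays unchanged. The 7-then-7 case is unaffected.

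Third, Section 2.1 expects every subject to respond below the DLT, so few may be affected. That may be so; the documents give no rate. But the Background says that nausea and diarrhea limit the oral dose to about 250 mg, so such events are foreseeable.

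A reader might also take the RASMET patient with moderate dizziness as a precedent for withdrawal on DLT: "This patient was withdrawn from the study and recovered spontaneously". The documents do not support that. They do not say that a DLT rule applied or that the event came before a prokinetic effect, and the patient was taking an alpha-adrenergic blocker.

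**Conclusion.** The point holds as two inconsistencies in safety wording that should be corrected. First, the stopping lists and the treat-on sentence allow opposite actions for one event, a difference of 0 versus up to 84 days of further dosing per affected subject. Second, the diarrhea DLT that is tabulated differs in count and duration from the one in the synopsis and 2.1 and from the 3.2 trigger, and the mismatch runs in both directions.

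The number of subjects affected is unknown. The conclusion rests on the text supplied. Section 11.2 defers analysis details to a separate SAP, which could settle the tabulated definition but would not tell sites whether to withdraw a subject.

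Three stronger inferences are not supported:
- *Subjects might be kept on a dose they cannot tolerate.* Under either reading, exposure at the DLT dose ends.
- *Uneven entry into the Fixed Dose Population distorts the results.* Section 11 assigns no analysis to that population; the safety, tolerability and primary efficacy analyses use the Safety Population.
- *The primary CSBM result is affected.* Nothing here shows that, and it is not claimed.

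The blood-pressure item is an overlap that needs a stated action. Abdominal pain, tabulated in 11.4 but not defined in 10.4, and the vomiting grade, which is open-ended in 2.1 but Grade 2 only in 10.4, are editorial.

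**What to change.** 1. In 2.1 and 10.15, replace the DLT item with: *stop escalation, step down to the highest DLT-free dose and fix; discontinue study drug if the DLT persists or no lower dose is available.* This agrees with 3.2 and covers a DLT at the lowest dose.
2. Use one diarrhea DLT, with the same count and duration, in the synopsis, 2.1, 3.2 and 10.4, and so in 11.4. Give the repeated-diarrhea sentence in 3.2 a count or delete it.
3. Keep systolic below 80 or diastolic below 40 mm Hg in 10.4 so that it is still tabulated, and state that it leads to discontinuation under 10.15 rather than step-down.
4. As editorial tidying, define abdominal pain in 10.4 or remove it from 11.4, and give vomiting one grade wording.

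The cost is amendment wording and site retraining, with no extra data or patients. There are two trade-offs. Some subjects whom a strict site would have withdrawn will stay on a lower dose; the discontinuation clause limits this. If the two-day diarrhea definition is chosen, single-day Grade 3 diarrhea no longer counts as a DLT, although it is still reported as an AE and falls within the Grade 3 or higher summary in 11.3. The sponsor could choose the one-day definition instead, but dose reduction would then have to follow it too.

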2.2. Primary Efficacy Objective and Endpoints

The primary efficacy objective of the study is to evaluate the effect of orally administered ENT-01 in improving constipation in subjects with Parkinson's disease-related constipation.

Primary Efficacy Endpoint

The primary efficacy endpoint of the study is to determine the change from baseline in weekly CSBM rate during the 12 weeks of the fixed dose period. Baseline weekly CSBM rate will be determined during the preceding randomized study.

2.3. Secondary Efficacy Objectives and Endpoints

The Secondary Efficacy Objectives of the study are:

- Change from baseline in the symptoms of Parkinson's disease
- Change from baseline in cognition
- Change from baseline in psychosis

[figure not shown]
Secondary Efficacy Endpoints will include the following:

- Change from baseline in the MDS-UPDRS Parts 1-3 score at the end of the 12-week fixed dose period. Baseline is defined as the MDS-UPDRS score at the screening Visit of this roll-over study.
- Change from baseline in cognition will be assessed by MMSE scores at the end of the 12-week fixed dose period. Baseline is defined as the MMSE score at the screening Visit of this roll-over study.
- Change from baseline in psychosis as assessed by the SAPS-PD at the end of the 12-week fixed dose period. Baseline is defined as the SAPS-PD score at the screening Visit of this study.

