2. To protect the rights, safety, and welfare of the participants in the study
3. To provide oversight to all personnel to whom study activities have been delegated
4. To maintain control all investigational product (IP) provided by the Sponsor and to maintain records of the disposition of those products
5. To conduct the study in accordance with the protocol amendment and all applicable local and national regulations, including, but not limited to, the International Conference on Harmonization (ICH) Guideline for Good Clinical Practice (GCP), and the standards set forth by the ethical principles that have their origin in the Declaration of Helsinki, GCPs as indicated in Food and Drug Administration (FDA), ICH E6 (R2) and ICH E3
6. To obtain approval for the protocol, protocol amendment, and all written materials provided to participants prior to initiating the study at my site
7. To obtain informed consent from all participants enrolled at my study site prior to initiating any study-specific procedures or administering IP to participants
8. To maintain accurate records of each patient’s participation.

Investigator's Signature

Date

STUDY SYNOPSIS

Study Title	A Multicenter, Non-Randomized, Open-Label Study to Evaluate the Safety and Efficacy of Orally Administered ENT-01 in Improving Constipation and Neurological Symptoms in Patients with Parkinson's disease and Constipation over a 14-week Period.
Protocol Number	ENT-01-2b-20-02
Study Phase	Phase 2b Follow-on study.
Methodology	This study will be conducted as an open-label safety follow-on to a multi-center, double-blind, randomized study. Dosing duration will be approximately 14 weeks. All subjects who participated in the randomized study will be offered participation in this unblinded, single-arm, safety study. ENT-01 will be administered daily in escalating doses followed by a fixed-dose for 12 weeks. The study will be conducted on an out-patient or in-patient basis with visits performed at the screening visit, at 6 and 12 weeks, and at the end of the 6th week of the wash-out period (end of study).
Study Duration	Each subject will participate for approximately 20 weeks: the dose escalation period lasting up to 20 days, the fixed dose period lasting 12 weeks, and the wash-out period lasting 6 weeks.
Study Centers	This is a multi-center trial with approximately 20 sites.

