motor and non-motor symptoms showed significant improvement. Improvement was also seen in the motor component. Improvements were also seen in cognitive function (MMSE scores), hallucinations, REM-behavior disorder (RBD) and sleep. Six of the patients enrolled had daily hallucinations or delusions and these improved or disappeared during treatment in five. RBD and total sleep time also improved progressively in a dose-dependent manner.

Most indices related to bowel function returned to baseline value by the end of the 2-week wash-out period while improvement in the CNS symptoms persisted. The rapid improvement in certain CNS symptoms is consistent with a mechanism whereby nerve impulses initiated from the ENS following ENT-01 administration augment afferent neural signaling to the CNS. This may stimulate the clearance of α S aggregates within the afferent neurons themselves as well as the secondary and tertiary neurons projecting rostrally within the CNS, since it is known that neural stimulation is accompanied by increased neuronal autophagic activity. We speculate that after cessation of ENT-01 administration, the neurons of the CNS would gradually re-accumulate an α S burden either locally or via trafficking from α S re-aggregation within the gut.

We are currently evaluating ENT-01 as a therapeutic to treat the constipation and neurologic symptoms associated with Parkinson's disease in a randomized Phase 2b (KARMET) study. Like the Phase 2a study, the randomized Phase 2b study has dosing between 75mg and 250mg and a treatment period limited to 25 days. This safety roll-over study is for patients who have completed the Phase 2b study, extending the treatment period for up to 14 weeks.

We recently completed a 19-week dog and 26-week rat study. There were no safety concerns specifically in relation to the GI tract.

Study rationale:

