The results of the study indicated that orally administered ENT-01 was safe and significantly improved bowel function and neurologic symptoms. Minimal systemic absorption suggests that improvements result from local stimulation of the ENS.

A randomized, placebo-controlled Phase 2b study (KARMET) of orally administered ENT-01 is currently being conducted in patients with PD and constipation. Dosing is daily, beginning at either 75 mg (baseline CSBM 1.0-3.0) or 150 mg (baseline CSBM 0-0.9) and escalating by 25 mg every 3 days until pro-kinetic effect or a maximum dose of 250 mg. Total treatment duration is 25 days.

A top-line data cut of the first 57 patients (an extension study is currently being performed) showed that ENT-01 achieved the primary efficacy endpoint in the treatment of constipation, with CSBM frequency increasing from 1.0 at baseline to 4.8 at the end of the fixed dosing period. Six patients exhibited hallucinations and/or delusions at the beginning of the study. These neurological symptoms disappeared or improved in 5 subjects randomized to ENT-01 but not in the 1 placebo patient. The dose required for improvement or disappearance of these neurological symptoms was patient specific. There were also improvements in other CNS parameters, including motor symptoms and memory.

Many of the AE were confined to the GI tract and were mild to moderate. Common adverse events included nausea in 10/53 (18.3%), diarrhea in 4/53 (7.4%), and abdominal pain in 4/53 (7.4%). There were 4 SAEs, 2 hospitalizations for joint replacement (1 patient on ENT-01 and 1 on placebo), 1 hospitalization for cholecystectomy and 1 for diuretic induced hypokalemia with weakness. Two of the 6 falls in the ENT-01 group occurred during the treatment period, the other

4 did not. In both cases the patient had a prior history of falls. The study is on-going, and a study report will be filed at the conclusion of the study.

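### Week-12 SAPS-PD change is a secondary endpoint, but subjects scoring 0 at roll-over screening are never re-rated, so relapse cannot show on the scale and the analysed subset is selected on a positive baseline

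*Combined protocol and SAP*

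**What the plan says.** The title covers "Safety and Efficacy of Orally Administered ENT-01 in Improving Constipation and Neurological Symptoms", and the three neurological scales make up the whole secondary efficacy set. In Section 2.3, "Baseline is defined as the MDS-UPDRS score at the screening Visit of this roll-over study"; MMSE and SAPS-PD have parallel definitions. The primary bowel endpoint instead uses the KARMET baseline (Sections 2.2 and 11.5).

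Section 3.2 has SAPS-PD rated in all subjects at Visit 1 and restricts later ratings to those with a positive screening score. Sections 3.3 to 3.6 and the footnote to Appendix 2 repeat the restriction for Visits 2 to 5. Section 11.5 runs the primary MMRM on the Safety Population and gives the secondary endpoints the same methodology. It has no rule for subjects who score 0 at screening and names no split by prior KARMET arm. Section 11.2 defers detail to a separate SAP, which is not among the documents reviewed.

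Entry is allowed on the day of the last KARMET visit and at any time after it (Sections 3 and 3.1). Within 14 days of that visit, procedures shared by the two studies need not be redone.

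On earlier results, Section 1 reports that in Phase 2a most bowel indices "returned to baseline value by the end of the 2-week wash-out period while improvement in the CNS symptoms persisted", and that "Significant and lasting improvements were observed in total MDS-UPDRS scores", with Part III and MMSE in the same sentence. For the first 57 KARMET patients it reports six with hallucinations or delusions: "These neurological symptoms disappeared or improved in 5 subjects randomized to ENT-01 but not in the 1 placebo patient". It adds: "There were also improvements in other CNS parameters, including motor symptoms and memory".

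**The concern.** An endpoint defined as change at week 12 needs a week-12 score. For SAPS-PD the protocol withholds that score from everyone at 0 on entry. This study draws on subjects who may already have responded to the same drug, so some zeros may be cleared psychosis rather than absence of psychosis. Those subjects would best show, on the scale, whether resolved psychosis stays resolved over 12 weeks.

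The rule also shapes the estimate. A subject at 0 can only stay level or worsen, and all such subjects are left out. Those kept were chosen because the score that serves as their baseline was positive, so their mean would tend to fall on re-rating even without a drug effect. Both features push the reported change towards improvement, and there is no concurrent control against which to judge it.

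A second, weaker worry concerns all three scales. If neurological benefit outlasts dosing, the screening score of a former ENT-01 subject may already include some of it. A pooled change would then mix first exposure with re-exposure in proportions set by who chose to roll over.

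**Working it through.** **Figures the plan states.** None bears on this point. The sample-size statement (Section 11.7) concerns adverse events and reproduces: 1 − 0.95^50 = 0.923, against 92%. Completers: 50 × (1 − 0.20) = 40, as in Section 4.

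**What the rating rule yields.**

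| Subject | Screening SAPS-PD | Rated at Visit 4 | Week-12 change |
|---|---|---|---|
| Psychosis still present | above 0 | yes | available |
| Psychosis cleared in KARMET | 0 | no | none |
| Cleared, relapsed before a late entry | above 0 | yes | available |
| Never had psychosis | 0 | no | none |

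With change as the response, a subject with no post-screening rating contributes nothing to an MMRM. Section 11.5 does not say whether such subjects are omitted or counted as unchanged.

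**How many cleared subjects (illustration).** Inputs: 6 of 57 with hallucinations or delusions (Section 1); 50 subjects; uptake of 75% from ENT-01 and 50% from placebo (Section 3). Assumptions: KARMET allocation r:1 with r = 1 to 3 (not stated in the documents), equal uptake with and without psychosis, and recorded hallucinations or delusions standing in for a positive score.

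- Psychosis at KARMET entry: 50 × 6/57 = 5.3.
- Former ENT-01 share: w = 0.75r / (0.75r + 0.50) = 0.60, 0.75, 0.82 for r = 1, 2, 3.
- Former ENT-01 subjects with psychosis at entry: 5.3 × w = 3.2, 3.9, 4.3.
- Section 1 does not separate disappearance from improvement, so the cleared fraction is anything from 0 to 1. Cleared subjects without a week-12 score: 0 to about 4 of 50. Among 40 completers the upper end is 2.5, 3.2, 3.4.

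The count is small, but so is its base. If all had cleared, the rated set from this group would fall from about 5 to about 2 (5.3 − 3.2, r = 1) or 1 (5.3 − 4.3, r = 3). The other 45 or so (50 − 5.3), without psychosis at KARMET entry, would also go unrated if they score 0 at screening.

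**Secondary point: persisting benefit at screening (illustration).** Let c be the fraction of the effect still present at screening in former ENT-01 subjects, and assume re-treatment restores the same full effect. Pooled change as a share of first-exposure change is 1 − w × c:

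| c | r = 1 | r = 2 | r = 3 |
|---|---|---|---|
| 0 | 100% | 100% | 100% |
| 0.5 | 70% | 62% | 59% |
| 1 | 40% | 25% | 18% |

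The documents do not give c. If re-treatment adds a full further effect, there is no understatement.

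Completers by prior arm, 40w and 40(1 − w), run from 24 and 16 (r = 1) to 33 and 7 (r = 3). The 95% half-widths, t(0.975, n − 1)/√n in SDs of change, are 0.42 and 0.53, then 0.35 and 0.92, against 0.32 for all 40. By-arm results would be descriptive only.

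**The case against.** A reader might infer that relapse of psychosis goes wholly unrecorded. The documents do not support that. Adverse events are assessed at every visit, Section 10.8 includes worsening of concomitant illness and events tied to underlying disease, and Section 10.6 counts an event absent before dosing as treatment-emergent. MDS-UPDRS Parts I-III, which cover non-motor symptoms, are rated in everyone at all five visits. What is lost is the SAPS-PD score itself, on the scale named in the endpoint.

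A reader might also infer that the KARMET responders described in Section 1 are the people who will go unrated. Those results come from the first 57 patients, while eligibility here is limited to Stage 2 Extension subjects, who may be different people. They show only that clearing is plausible.

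On baseline, a tempting reading is that the screening visit is the wrong reference. It is not. With an unlimited lag in a progressive disease, a contemporaneous baseline is defensible and validly measures incremental change; a KARMET score could be old and mix in progression and changes in other medication. Nor is carry-over demonstrated. The Phase 2a evidence follows a 2-week wash-out, the interval from last KARMET dose to final visit is not given, and the sponsor itself speculates that "after cessation of ENT-01 administration, the neurons of the CNS would gradually re-accumulate" an alpha-synuclein burden. Carry-over alone would understate benefit, not inflate it.

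Finally, the separate SAP may already provide a prior-arm summary, the study is sized on adverse events, and no stated decision depends on these scales. All of this limits the second point. It does not answer the first: a SAP cannot recover a rating that was not taken.

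**Conclusion.** The SAPS-PD point stands on the text and needs no assumption: the visit sections and Appendix 2 agree, and a screening score of 0 means no week-12 score. The result will describe change only in subjects selected for a positive score, with regression to the mean built in and no sight of worsening from 0. The number who cleared in KARMET and are then unrated is probably small, 0 to about 4 of 50, given the 6/57 rate, the stated uptake and an assumed 1:1 to 3:1 allocation. It is a modest defect in a secondary endpoint, but cheap to cure and irrecoverable once Visit 4 has passed.

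The baseline point is a lower-priority reporting matter. Persisting KARMET benefit in former ENT-01 subjects is inferred from Phase 2a and its size is unknown; the 18% to 100% range above reflects its assumptions, not evidence. No claim that the screening baseline is invalid, or that a prior-arm analysis is definitely missing, is justified.

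**What to change.** In Section 3.5 and Appendix 2, extend the Visit 4 SAPS-PD rating at least to subjects who scored above 0 at KARMET baseline or, if KARMET did not use the scale, had hallucinations or delusions recorded then. Preferably rate all subjects at Visit 4, which also removes the selection on a positive score. In Section 11.5, state how screening scores of 0 enter the analysis. The cost is a protocol amendment and, in the minimum version, a few extra ratings at an existing visit; rating everyone adds one per subject who scored 0. KARMET baseline records are needed, but not arm codes, so this need not wait for unblinding and should precede further Visit 4 attendances.

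At lower priority, keep the screening baseline and label it incremental change. Unless the separate SAP already does so, add to Section 11.5 a descriptive summary of the three scales by prior KARMET arm, showing time since last KARMET dose, and a supportive change from the KARMET pre-treatment score where that scale was collected. This needs KARMET arm codes and neurological scores. KARMET is double-blind, and Section 1 says of it "The study is on-going, and a study report will be filed at the conclusion of the study", so these tables must wait for its unblinding. With possibly about 7 former placebo completers, they are for description, not testing.
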